1.4 Risk/Benefit assessment

This is an exploratory study to evaluate on psoriasis mini-zones the safety, efficacy, of CD10367 topical solution at 1% and 3%. As only mini-zones will be treated in this study no individual benefit is expected for the subjects who will participate to the study.

Protocol No.: RD.03.SPR.112075 V01 16 Aug 2016

Page 25 of 85

All investigational medicinal product (IMP) will be applied on mini-zones, located on psoriatic plaques, and the quantity applied will be under the control of the qualified staff who will perform all the applications at the site and no IMP will be given to the subjects for applications at home.

In order to improve the drug penetration, in this study, one or two psoriasis plaque(s) will be desquamated using a marketed cosmetic keratolytic agent containing urea and low concentration of salicylic acid prior to application of CD10367 and its placebo on mini-zones. In clinical practice, urea and salicylic acid-based products are usually associated with local psoriasis treatments in order to increase and fasten their efficacy. Only mild irritation has been reported as the most common side effect, making urea a safe and well-tolerated topical drug (Pan, 2013; Jacobi, 2015). This keratolytic product will be applied twice daily by the subjects at home.

The safety ratios calculation for the current study were estimated using two approaches: 1) in accordance with regulatory guidance (FDA Guidance for Industry July 2005), CCI

CCI		

Protocol No.: RD.03.SPR.112075 V01 16 Aug 2016

Page 26 of 85

Considering the estimated safety ratios for the proposed study and the short treatment duration, these safety risks are not expected to occur. However, appropriate inclusion/ exclusion criteria and safety follow-up measures have been planned.

Regarding the ocular toxicity risk, even if clinical studies done by AZ and GRD did not confirm this risk in human being, specific inclusion/exclusion criteria have been defined to minimize this risk for the subjects, e.g. exclusion of subjects with abnormal ophthalmic examination according to the ophthalmologist at Screening, etc.

As to the cardiac risk, an ECG is planned at screening with exclusion of subjects with any clinically significant ECG findings; an ECG monitoring is planned during the study.

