7.2.5 Local tolerability assessment

Local tolerability assessment will be performed using the following twice a week from Day2 to Day 19/ET visits scales two times per week during the treatment period. If at any visit, a treatment leads to discontinue applications either temporarily or permanently, an AE must be declared, and local tolerability assessments and photos of the concerned zone must be performed even if it was not planned in study flowchart for this visit. Grading for local tolerability assessments will take into consideration the time period from the last local tolerability assessment up to the current visit. The worst severity since the previous visit will be recorded. Local tolerability (Irritation, stinging/burning, pruritus) will be assessed separately on each minizone using the following scales:

Protocol No.: RD.03.SPR.112075 V01 16 Aug 2016

Page 52 of 85

Table 7 Local tolerance 4-point scales

Irritation	Skin irritati	n Assessment						
0	None:	o signs of irritation						
1	Mild:	Slight signs of irritation						
2	Moderate:	Moderate signs of irritation: Obvious increase in redness as compared to the non-treated surrounding area						
3	Severe:	Severe signs of irritation						
Stinging/ Burning	Prickling p	ain sensation						
0	None:	No stinging/burning						
1	Mild:	Slight warm, tingling/stinging sensation; not really bothersome						
2	Moderate:	Definite warm, tingling/stinging sensation that is somewhat bothersome						
3	Severe:	Hot, tingling/stinging sensation that causes severe discomfort						
Pruritus	Itch sensat	tion						
0	None:	No itching						
1	Mild:	Itching is noticeable but not really bothersome						
2	Moderate:	Definite itching that is somewhat bothersome						
3	Severe:	Marked itching, urge to scratch and causes definite discomfort						

Irritation, will be clinically evaluated by the Investigator. The Investigator will record stinging/burning and pruritus after discussion with the subject. The severity of stinging/burning sensation occurring after the last drug application before the visit will be asked. The Investigator will ask an open-ended question, taking care not to influence the subject's answer, such as "Have you experienced any sensations such as stinging/burning?"

An Adverse Event page must be completed if the severity of the signs and symptoms is such that:

- The subject temporary or permanently discontinues the treatment at his/her request or at the Investigator's request.

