8.1.2 Baseline visit [Day 1]

At the Baseline visit, the Investigator or designee will:

- 1. Ask the subject about AEs using an open-ended question, such as "Have you noticed any change in your health since the last visit?" Record all events, as appropriate, on the corresponding CRF form(s).
- 2. Check laboratory results hematology, biochemistry, virology, urinalysis from the Screening visit.
- 3. Ask the subject about any changes in his/her concomitant therapies/procedures (added, removed or changed) since the previous visit. Record all changes in the source document and the CRF.
- 4. Check vital signs
- 5. Confirm the six target mini-zones according to the inclusion criteria,

For non-desquamated zones TSS (erythema + induration + scaling) should be superior or equal to 6 on a 13 point scale (0 to 12), with individual score of erythema, induration and scaling separately being ≥ 2 . The zones must present a similar severity, i.e.: identical Baseline TSS or variation of ± 1 grade.

For desquamated zones scaling score should be equal to 0 or 1 on a 5 point scale (0 to 4), and individual score of erythema, and induration separately being ≥ 2 . The zones must present a similar severity, i.e.: identical Baseline sum of erythema and induration or variation of ± 1 grade.

- 8. Confirm subject meets inclusion/exclusion criteria.
- 9. Assign a randomization number to the Subject (this number will be assigned to randomized Subjects in increasing order and no numbers will be omitted).

10.

A member of staff other than the Investigator will:

- 11. Apply 50µl of the tested products on the Subject's selected mini-zones according to the randomization list generated by the sponsor and in compliance with the operational manual.
- 12. Instruct the Subject to avoid wetting areas (swimming, bath, sauna, hammam are not allowed). However, showers are permitted at least eight hours following applications.
- 13. Complete the Subject Enrollment Log and subject identification code list.
- 14. Schedule the next visits (D2 to D19).

nternally Approved 01-Feb-2019

CONFIDENTIAL GALDERMA

Protocol No.: RD.03.SPR.112075 V01 16 Aug 2016

Page 70 of 85

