8.1.3 Interim visits (from Day 2 to Day 18)

At each of the following visits, Subjects will be asked to return to the clinical centre every day (except Saturdays and Sundays) for study drug applications and site evaluations.

At each visit, the Investigator or the designated study person will:

- 1. Ask the Subject about AEs by asking an open-ended question taking care not to influence the Subject's answer, such as "Have you noticed any change in your health since the last visit?" Record all events, as appropriate on the corresponding CRF pages.
- 2. Ask the Subject whether there have been any changes to his/her concomitant therapies/procedures (added, removed, or changed) since the previous visit. Document all changes on the Concomitant Therapy form of the CRF.

A member of staff other than the Investigator will:

- 3. Apply 50 µl of the tested products on the Subject's selected mini-zones according to the randomization list and in compliance with the operational manual
- 4. Instruct the Subject to avoid wetting areas (swimming, bath, sauna, hammam are not allowed). However, showers are permitted at least eight hours following applications.
- 5. Schedule an appointment for the next Visit

Moreover at Day 2, the Investigator, before any applications will:

6. Assess local cutaneous tolerance of each mini-zone.

Also at Day 4, Day 8, Day 11, Day 15 the Investigator, before any applications will:

- 7. Assess local cutaneous tolerance of each mini-zone.
- 8. Perform clinical evaluations of efficacy by measuring the intensity of the erythema, scaling and induration on each individual mini-zone.
- 9. Perform clinical evaluations of the clearing score for each mini-zone

Moreover at Day 5 visit:

10. Collect a blood sample for plasma PK analysis.

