9.1.3 Data presentation and graphics

The subject disposition, demographics, baseline characteristics, previous therapies, concomitant therapies will be summarized by descriptive statistics.

All efficacy variables will also be summarized by treatment (treatment / pre-treatment) at each visit. The categorical variables will be summarized by frequency and percentage for each response category (N, %). The continuous variables will be summarized using means, medians, minimum, maximum, and standard deviations for the data collected at each visit.

The area under the curve of the TSS (sum of individual clinical scores erythema, induration/plaque elevation and scaling), as well as those of each individual clinical score will be calculated from Day 1 (before application) up to Day 19 by subject and by treatment, using the trapezoidal rule.

The time to success (defined as a clearing score of 0 or 1) will be summarized by treatment. Only the earliest day of success will be considered in defining the time to partial clearing, independently of the subsequent days.

The local tolerance scores will be summarized using frequency and percentage by visit and study product. The worst scores will also be summarized.

Adverse Events will be tabulated by study treatment. Adverse Events will be tabulated in frequency tables by System Organ Class (SOC) and Preferred Term (PT) based on the MedDRA dictionary. Additional summary tables will be provided for Adverse Events that will be considered as severe, serious (SAEs) and Adverse Events leading to discontinuation. Any AE and related AE will be summarized for each category. Analyses of adverse events will be based on Treatment Emergent Signs and Symptoms (TESS) *i.e.* adverse events occurring on the day of, or after, treatment application (Baseline).

Events having occurred before the day of treatment application (i.e. before Baseline) will be listed only.

Due to the intra-individual study design and whenever possible (known from e-CRF), AE will be imputed to the treated area, when not possible then the AE will be imputed to all treated area.

Physical examination, vital signs, ECG and ophthalmic examination will be summarized by descriptive statistics.

Shift tables for the laboratory data (and urinalysis) will be tabulated for each laboratory parameter.

Protocol No.: RD.03.SPR.112075 V01 16 Aug 2016

Page 75 of 85

Pharmacokinetics parameters will be descriptively summarized.

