7.3.2. Local tolerance

Local individual signs/symptoms (irritation, skinging/burning, pruritus) in term of frequency distribution and in quantitative description and the worst score (from Day 2 to Day 19/ET) over time of each individual sign/symptom will be calculated by study product.

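### Local tolerance has no pre-dose score, so signs present before the first application, chiefly pruritus, enter each product's absolute tolerance rates

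*Protocol*

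**What the plan says.** **Timing.** Protocol 7.2.5: "Local tolerability assessment will be performed using the following twice a week from Day2 to Day 19/ET visits". Section 8.1.3 places the first score: "Moreover at Day 2, the Investigator, before any applications will" assess each mini-zone. That is one day after the first application. The local tolerance row is blank at Day 1 both in protocol Table 2 and in the SAP schedule (section 3). Erythema, scaling and induration are graded on the same zones at that visit.

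**What is recorded.** Section 7.2.5 has irritation, stinging/burning and pruritus graded 0 to 3 on each zone. "Grading for local tolerability assessments will take into consideration the time period from the last local tolerability assessment up to the current visit". The next instruction is: "The worst severity since the previous visit will be recorded".

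**Analysis.** Protocol 9.1.3: "The local tolerance scores will be summarized using frequency and percentage by visit and study product"; worst scores are also summarised. SAP 7.3.2 says that "the worst score (from Day 2 to Day 19/ET) over time of each individual sign/symptom will be calculated by study product". The irritation table shell in SAP 9.3.2 starts at Day 2. No visible text plans a change from a pre-dose value or a new-onset rule for these scores.

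**State of the zones before dosing.** At Baseline the desquamated zones need "individual score of erythema, and induration separately being ≥ 2" (protocol 8.1.2), and the other four zones have the same minimum on all three clinical items. For the two pre-treated zones, protocol 1.4 adds: "This keratolytic product will be applied twice daily by the subjects at home". The same section names mild irritation as the product's commonest side effect. Section 8.2 stops its use only on the day of Baseline.

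**The concern.** The tolerability scales grade a state, not a change. A zone that itched at grade 1 before the study and still itches at grade 1 on Day 2 gives that product a worst score of 1. Pre-dose signs are foreseeable here: all six zones are active psoriasis, and two have just had one to two weeks of a 50% urea / 2% salicylic acid cream.

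Safety stands beside efficacy in the primary objective, and protocol 2.2 hypothesises that the solutions are well tolerated. By-product tolerance rates are therefore likely to be read at face value. The SAP gives other measures a reference value: Day 1 for the efficacy scores (7.2.5.1), and baseline or screening for vital signs, QTc and laboratory values (7.3.4, 7.3.6, 7.3.8). Local tolerance has none, and a pre-dose score that was not taken cannot be recovered later.

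**Working it through.** The plan states no figure on this point, so the check is mainly a reading of the documents, followed by an illustration.

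**Step 1. Could a Day 1 score exist elsewhere?** Some Baseline steps in protocol 8.1.2 are missing from the released text. However, 7.2.5, 8.1.3 and both schedules all start at Day 2, so a hidden routine Day 1 score is unlikely. Footnote c to Table 2 asks for a tolerance score when an adverse event occurs in a treatment zone. That could capture declared keratolytic irritation at Day 1, but not milder signs.

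**Step 2. Which items can carry a pre-dose sign forward?**

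| Item | Anchor in 7.2.5 | Exposure to the problem |
|---|---|---|
| Pruritus | None | Full |
| Irritation | Grade 2 is judged against untreated skin around the zone, without saying whether that skin is plaque; grades 1 and 3 have no such anchor | Partial; clearest for mild irritation after the keratolytic |
| Stinging/burning | Asked for the time after the last application | Small; persisting burning still counts |

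The look-back at Day 2 does not remove the problem. No tolerability assessment precedes Day 2. If the window is taken to start at the previous visit (Day 1), a sign that persists past that visit is still recorded.

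**Step 3. Illustration of the effect on an any-sign summary.** The inputs are assumptions, not document figures: *b* is the share of zones with a pre-dose sign that persists, *t* the true product-induced rate, *v* the true vehicle-induced rate. Each product and skin condition has 24 zones (24 planned subjects, one zone each).

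Observed rate = 1 − (1 − b)(1 − t). Observed difference from vehicle = (1 − b)(t − v).

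| b | Zones affected if t = 0 (24 × b) | Active rate, t = 10% | Vehicle rate, v = 0 | Observed difference (true 10 points) |
|---|---|---|---|---|
| 10% | 2.4 | 1 − 0.9 × 0.9 = 19% | 10% | 9 points |
| 30% | 7.2 | 1 − 0.7 × 0.9 = 37% | 30% | 7 points |
| 50% | 12.0 | 1 − 0.5 × 0.9 = 55% | 50% | 5 points |
| 70% | 16.8 | 1 − 0.3 × 0.9 = 73% | 70% | 3 points |

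The absolute rate rises with *b* for every product. The difference shrinks but keeps its sign.

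**Step 4. Does the planned summary behave this way?** Only in part. The formula collapses the scale to 0 versus 1 or more. The SAP shells show all four grades and the mean, so a move from 1 to 2 or 3 stays visible. If a product adds *d* to the mean grade whatever the starting level, the mean active-minus-vehicle difference remains *d*, except near the ceiling of 3.

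**Step 5. Would change from Day 1 be enough alone?** Not on the pre-treated zones. Suppose both zones score 1 on Day 1 from the keratolytic and that irritation then fades. A product that itself causes grade 1 irritation shows 1 − 1 = 0 change, which looks clean. Its vehicle zone shows 0 − 1 = −1. The difference of 1 between the paired zones recovers the signal, so both summaries are needed.

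**The case against.** The strongest defence is the within-subject control. Every subject has a vehicle zone on standard and on desquamated skin (protocol 3.1, 3.2.3), products are applied according to the randomisation list, and the tolerance shells put vehicle and active columns side by side. A reader might infer that keratolytic and drug irritation cannot be separated. The documents do not support that: pre-treated 3% against pre-treated vehicle separates them, because both zones had the same keratolytic. This defence stands for CD10367 comparisons, with limits. Section 3.2.3 names the vehicle as control for efficacy, no tolerance contrast is described in the visible text, and Betneval ointment has no vehicle of its own.

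A reader might also infer that all pre-existing itch, burning and redness is booked as product intolerance, or that rates are inflated several-fold. The anchors in Step 2 contradict the first for two of the three items. The second needs pre-dose and true rates that the documents do not give, and a yes/no summary that the SAP does not plan.

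Adverse events are also protected. They are judged against the condition at the first visit (7.2.6.1.1), causality is assessed separately for drug and procedure (7.2.6.1.7), and pre-treatment events are reported apart (SAP 7.3.3). The weakness is therefore confined to the tolerance score tables. Finally, this is an exploratory study with no visible test or decision rule on these scores, which lowers the stakes. None of this supplies a pre-dose reference for pruritus or for the absolute by-product rates.

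**Conclusion.** The point holds in limited form. Without a pre-dose score, the absolute tolerance rates for each product include signs that were there before dosing. This chiefly concerns pruritus on all zones and mild irritation on the two keratolytic-treated zones. The active-versus-vehicle comparison is at most diluted, and graded or mean summaries may show little dilution.

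The size cannot be estimated from the documents, and the trial as planned would not measure it. The Step 3 range (2.4 to 16.8 affected zones of 24 for a product that causes nothing; a true 10-point excess shown as 9 to 3 points) rests entirely on assumed pre-dose rates of 10% to 70%, persistence to Day 2 and an any-sign summary. To infer that the tolerability assessment is invalid would go beyond the documents. This is a cheap improvement to a stated primary objective.

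**What to change.** 1. **Protocol Table 2, 7.2.5 and 8.1.2:** score irritation, stinging/burning and pruritus on all six zones at Day 1 before the first application. Word the stinging/burning question at that visit for current sensation, since no study drug has yet been applied.
2. **SAP 7.3.2 and the 9.3.2 shells:** beside the raw worst score, add the worst increase after Day 1 (new onset or worsening) by product.
3. **Same SAP section:** add the within-subject difference from the vehicle zone in the same skin condition. Show it by visit as well as for the worst score, because keratolytic irritation may fade after Day 1. Betneval has no vehicle of its own, so its main reference would be the Day 1 score.

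**Cost:** 3 items × 6 zones = 18 short ratings per subject (18 × 24 = 432 over the planned trial), at a visit where the same zones are already graded, plus one CRF page and one added summary. No extra visit or procedure is needed.

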7.2.6 Adverse Events

Adverse events (AEs) are to be monitored throughout the course of the clinical trial. All AEs are to be reported on the Adverse Event Form of the CRF with complete information as required. If AEs occur, the main concern will be the safety of the subjects. At the time of the ICF signature, each subject must be provided with the name and phone number of clinical trial center personnel for reporting AEs and medical emergencies.

Protocol No.: RD.03.SPR.112075 V01 16 Aug 2016

Page 53 of 85

7.2.6.1 Definitions

7.2.6.1.1 *Adverse events (AE)*

According to ICH E2A, an AE is any untoward medical occurrence in a subject or clinical investigation subject administered a pharmaceutical product and which does not necessarily have a causal relationship with this treatment. An AE can therefore be any unfavorable and unintended sign (including an abnormal laboratory value), symptom, or disease temporally associated with the use of a medicinal (investigational) product, whether or not related to the medicinal (investigational) product.

Thus any new sign, symptom or disease, or any clinically significant worsening of an existing sign, symptom or disease compared to the condition at the first visit (including disease treated), should be considered as an AE. Lack of efficacy is not considered as an AE.

Each new episode of a chronic disease (e.g., hay fever, allergy, etc.) from the screening visit should be reported as a new AE.

Notes:

- Any new sign or symptom reported by the subject that appears after accidental or intentional overdose or misuse should also be reported as an AE.
- There should be an attempt to report a diagnosis rather than the signs, symptoms or abnormal laboratory values associated with the report of an AE. However, a diagnosis should be reported only if, in the Investigator's judgment, it is relatively certain. Otherwise, symptoms, signs, or laboratory values should be used to describe the AE.
- The "date of onset" should be the date that the first symptom occurred.

7.2.6.1.2 Serious Adverse events (SAE)

An SAE is any untoward medical occurrence that at any dose:

- Results in death,
- Is life-threatening,
- Requires inpatient hospitalization or prolongation of existing hospitalization,
- Results in persistent or significant disability/incapacity, or
- Is a congenital anomaly/birth defect.

Important medical events that may not result in death, be life-threatening, or require hospitalization may be considered an SAE when, based upon appropriate medical judgment, they may jeopardize the safety of the subject, and may require medical or surgical intervention to prevent one of the outcomes listed in this definition. Examples of such events are intensive treatment in an emergency room or at home for allergic bronchospasm, blood dyscrasia, or convulsions that do not result in hospitalization.

Protocol No.: RD.03.SPR.112075 V01 16 Aug 2016

Page 54 of 85

Note:

The term "life-threatening" refers to an event in which the subject was at risk of death at the time of the event; it does not refer to an event that hypothetically might have caused death if it was more severe

Inpatient hospitalization is considered to have occurred if the subject has had to stay for a night at the hospital. The criterion for prolongation of hospitalization is also defined as an extra night at the hospital. Hospitalization may not constitute sufficient grounds to be considered as an SAE if it is solely for the purpose of diagnostic tests (even if related to an AE), elective hospitalization for an intervention that was already planned before subject enrolment in the clinical trial, admission to a day-care facility, social admission (e.g., if the subject has no place to sleep), or administrative admission (e.g., for a yearly examination).

